8.2 Dose Modifications

- As a general approach, it is suggested that, when possible, all toxicities be managed with supportive care at the earliest sign of toxicity and modifying the dose as necessary.
- No dose reductions below level -2 are allowed. If dose reductions below 20 mg once daily are required (i.e. level -2), then cabozantinib/placebo will be discontinued.
- Cabozantinib/placebo will not be re-escalated once reduced.
- If cabozantinib/placebo is held for more than 4 weeks, then patients must discontinue protocol treatment. Any missed or delayed doses should be considered skipped, and the Study Calendar requirements in Section 5.0 should be maintained.
- If multiple adverse events are seen, administer dose based on the greatest reduction required for any single adverse event observed. Reductions apply to treatment given in the preceding cycle and are based on adverse events observed since the prior dose.
- If more than one of these apply, use the most stringent (i.e. the greatest dose reduction).
- AERS reporting may be required for some adverse events (see Section 9.0).

• **NOTE**: PRO-CTAE data should not be used for determining attribution, dose modifications, or reporting serious adverse events.

8.2.1 Dose Levels

Dose Level	Cabozantinib/Placebo		
0*	60 mg once daily		
-1	40 mg once daily		
-2	20 mg once daily		

^{*}Dose level 0 refers to the starting dose

8.2.2 Hematologic Toxicities

For grade 3 neutropenia with documented infection, grade 3 neutropenia \geq 5 days, or grade 4 neutropenia, delay cabozantinib/placebo until toxicity resolves to grade \leq 1, then resume cabozantinib/placebo with one dose level reduction.

For grade 3 febrile neutropenia, delay cabozantinib/placebo until ANC grade ≤ 1 and temperature to ≤ 38.0 °C, then resume cabozantinib/placebo with one dose level reduction.

For grade 4 febrile neutropenia, discontinue cabozantinib/placebo.

For grade 3 thrombocytopenia with clinically significant bleeding or grade 4 thrombocytopenia, delay cabozantinib/placebo until platelet count $\geq 100,000/\text{mm}^3$, then resume cabozantinib/placebo with one dose level reduction.

For **grade 4 anemia**, delay cabozantinib/placebo and use supportive care (e.g. red blood cell transfusions) as clinically indicated according to institutional guidelines until toxicity resolves to grade ≤ 1 , then resume cabozantinib/placebo with one dose level reduction.

For grade 4 hematologic toxicities other than anemia, discontinue cabozantinib/placebo.

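### Section 8.2.2 gives grade 4 neutropenia and grade 4 thrombocytopenia two incompatible actions, and the general rules in 8.2 do not clearly settle which applies

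*Combined protocol and SAP*

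**What the plan says.** Section 8.2.2 sets out event-specific rules and then a general line.

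- Neutropenia. The rule covers certain grade 3 cases and continues: "or grade 4 neutropenia, delay cabozantinib/placebo until toxicity resolves to grade" 1 or lower, after which drug restarts one dose level lower.
- Thrombocytopenia. The rule covers grade 3 with clinically significant bleeding and continues: "or grade 4 thrombocytopenia, delay cabozantinib/placebo until platelet count" is at least 100,000/mm³, after which drug restarts one dose level lower.
- Febrile neutropenia. "For grade 4 febrile neutropenia, discontinue cabozantinib/placebo".
- Grade 4 anemia. Hold, give supportive care, and restart one dose level lower on recovery.
- General line, last in the section. "For grade 4 hematologic toxicities other than anemia, discontinue cabozantinib/placebo".

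Four bullets in the opening list of section 8.2 bear on how these rules combine:

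- "If multiple adverse events are seen, administer dose based on the greatest reduction required for any single adverse event observed".
- "If more than one of these apply, use the most stringent (i.e. the greatest dose reduction").
- "If cabozantinib/placebo is held for more than 4 weeks, then patients must discontinue protocol treatment".
- "If dose reductions below 20 mg once daily are required (i.e. level -2), then cabozantinib/placebo will be discontinued".

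**The concern.** Grade 4 neutropenia and grade 4 thrombocytopenia each meet the terms of a hold-and-restart rule and also the terms of the general discontinuation line. If the general line controls, the two event-specific grade 4 instructions have no effect. If the event-specific rules control, the general line misdescribes its own coverage, because it names anemia as its only exception.

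At stake is whether a patient who has recovered from a grade 4 cytopenia goes back on study drug or stops for good. Two sites could decide this in opposite ways for the same event, each citing protocol text. The enhanced central monitoring in section 13.6 includes treatment records from the first two courses and can require a corrective action plan for significant deviations in treatment administration. With two rules on the page, it has no single standard to judge against. The protocol foresees these events: section 9.1.2 solicits and grades neutrophil and platelet decreases, and section 9.3.3 gives grade 3/4 hematosuppression its own reporting instruction.

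**Working it through.** No sample size, power or alpha figure is involved, so the check is a comparison of the text.

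**Step 1. Set each grade 4 event named in 8.2.2 against the general line.**

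| Grade 4 event | Event-specific action | General line | Result |
|---|---|---|---|
| Neutropenia | Hold, then restart one level lower | Discontinue | Conflict |
| Thrombocytopenia | Hold, then restart one level lower | Discontinue | Conflict |
| Febrile neutropenia | Discontinue | Discontinue | Same action twice |
| Anemia | Hold, then restart one level lower | Excepted | No conflict |

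Two of the four conflict.

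**Step 2. Could the general line be a residual rule for hematologic events not listed?** The text does not say so. Grade 4 anemia is itself listed above the line. A purely residual line would have no need to except it, so excepting anemia alone implies that the line reaches the other listed events. Where section 8.2 does intend a residual rule, it marks it: 8.2.17 limits its grade 4 non-hematologic rule to toxicities not already covered earlier. The hematologic line carries no such limit.

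**Step 3. Could the most-stringent bullet in 8.2 settle it?** The bullet just before it already deals with multiple adverse events, so this one may be meant for overlapping rules, which would point to discontinuation. Three things prevent a firm reading. The word standing for what may overlap has no clear referent. The gloss speaks of dose reduction and does not mention discontinuation. Applying the bullet would also empty the two grade 4 hold-and-restart instructions of effect, so 8.2.2 would still need correcting.

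**Step 4. When do the two actions lead to different outcomes?** Both stop drug at the event. The dose levels in 8.2.1 are 0 (60 mg), -1 (40 mg) and -2 (20 mg).

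- Level 0 or -1, hold of no more than 4 weeks: one rule restarts at -1 or -2 respectively; the other discontinues. The outcomes differ.
- Level -2: a further reduction would fall below 20 mg, so 8.2 discontinues under either rule.
- Any level, hold of more than 4 weeks: 8.2 discontinues under either rule.

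**Step 5. How many patients?** This cannot be computed. The CAEPR in section 9.4 (n = 3219) places platelet count decreased in its column for events at 20% or less, without regard to grade. It lists neutrophil count decreased among events with insufficient evidence of causation. The nursing guidelines in section 10.1 describe cytopenias as common. None of these is a grade 4 frequency.

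**Step 6. Does it reach the analysis?** Under section 12.1.3, patients who stop for a reason other than progression continue 12-weekly follow-up for progression and survival, and section 13.0 analyses efficacy by intention to treat. The conflict does not alter the recorded maximum grade of the event. Dose modification enters the planned analyses in section 14.2.4, under the second objective of the optional pharmacokinetic substudy.

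**The case against.** The best defence is that the general line is a catch-all for hematologic events not listed above it. The separate febrile neutropenia line supports this: if the general line already covered every grade 4 event except anemia, that line would be unnecessary. This is a fair point, but the anemia exception cuts the other way with at least equal force, because a catch-all would not need it. Under either reading some words in 8.2.2 are redundant, which shows that the section does not settle the matter.

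The second defence is that a site could reasonably apply the most-stringent bullet and discontinue. It could, but the two defences give opposite answers: the catch-all reading keeps hold-and-restart, and the bullet leads to discontinuation. A careful reader could arrive at either.

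The third objection is that the impact is narrow. This stands. The outcomes diverge in a limited set of patients, no frequency is available, section 7.1 directs treatment questions to the study contacts, and no consequence for PFS is shown. These points limit the weight of the finding without removing the contradiction. Case-by-case advice does not correct the written rule.

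**Conclusion.** The section is wrong as written. Two of the four grade 4 hematologic events it names carry actions that cannot both be followed, and neither the wording of the general line nor the bullets in 8.2 resolve them. The practical difference is confined to patients at level 0 or -1 who recover within 4 weeks, and the number of such patients is unknown. The consequence is for patient management and later drug exposure, not for the primary PFS analysis. The conclusion rests on the ordinary meaning of the text and on no outside figure. It should be fixed because it is a direct contradiction in a stopping rule and is cheap to remove. No view is taken on which action is correct.

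**What to change.** Reconcile section 8.2.2 by amendment so that:

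1. grade 4 neutropenia and grade 4 thrombocytopenia each have one stated action;
2. the last line says which grade 4 hematologic toxicities it covers;
3. section 8.2 says whether the most-stringent bullet applies when two rules cover a single event.

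The study team decides which action applies to each event. The cost is one or two sentences in an amendment and a memo to sites, with no change to data collection or analysis.

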8.2.3 Hepatic Toxicities

8.2.3.1 For patients with ALT or AST \leq ULN at the time of registration:

For grade 1 ALT or AST, continue cabozantinib/placebo and consider checking LFTs in two weeks.

For grade 2 ALT or AST, consider checking LFTs weekly. If ALT or AST continues to rise within grade 2, delay cabozantinib/placebo (and consider checking LFTs weekly) until grade ≤ 1 , then resume cabozantinib/placebo with one dose level reduction.

For **grade 3 ALT, AST, or bilirubin**, delay cabozantinib/placebo and check LFTs weekly until grade ≤ 1 , then resume cabozantinib/placebo with one dose level reduction. If LFT abnormalities are related to a biliary obstruction that has resolved and have returned to grade ≤ 1 , cabozantinib/placebo treatment may be resumed with the previous dose.

For grade 3 bilirubin recurring after a dose level reduction or grade 4 bilirubin without biliary obstruction, discontinue cabozantinib/placebo. If LFT abnormalities are related to a biliary obstruction that has resolved and values have returned to grade ≤ 1 , cabozantinib/placebo treatment may be resumed with the previous dose.

For grade 4 ALT or AST, discontinue cabozantinib/placebo.

For grade 3 or 4 hepatic failure, discontinue cabozantinib/placebo.

8.2.3.2 For patients with ALT or AST above the ULN but \leq 3.0 x ULN (i.e. grade 1) at the time of registration:

For \geq 1.5 fold increase of ALT or AST and both ALT and AST are \leq 5.0 x ULN, continue cabozantinib/placebo and consider weekly monitoring of LFTs. If LFTs continue to rise, delay cabozantinib/placebo (and consider checking LFTs weekly) until grade \leq 1, then resume cabozantinib/placebo with one dose level reduction.

For \geq 1.5 fold increase of ALT or AST and 5.0 < ALT or AST \leq 20.0 x ULN (i.e. either ALT or AST is grade 3), delay cabozantinib/placebo (and consider checking LFTs weekly) until grade \leq 1, then resume cabozantinib/placebo with one dose level reduction.

8.2.3.3 For all patients:

For ALT or AST increases accompanied by progressive elevations of total bilirubin and/or elevations of coagulation tests, delay cabozantinib/placebo (and consider checking LFTs weekly) until total bilirubin $< 1.5 \times ULN$, INR $< 1.5 \times ULN$, and ALT or AST grade ≤ 1 , then resume cabozantinib/placebo with one dose level reduction.

For ALT or AST increases accompanied by bilirubin > 2 x ULN in the absence of biliary obstruction or other explanation, discontinue cabozantinib/placebo.

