3.3.2 Not pregnant and not nursing

Women of childbearing potential must have a negative pregnancy test done \leq 14 days prior to re-registration.

A female of childbearing potential is a sexually mature female who: 1) has not undergone a hysterectomy or bilateral oophorectomy; or 2) has not been naturally postmenopausal for at least 12 consecutive months (i.e. has had menses at any time in the preceding 12 consecutive months).

3.3.3 Required Laboratory Values:

Absolute Neutrophil Count (ANC) $\geq 1,500/\text{mm}^3$

Hemoglobin $\geq 9 \text{ g/dL}$

^{*}Except in the case of Gilbert disease, in which case Total Bilirubin must be $\leq 3 \times ULN$

^{**}Supplementation is acceptable to achieve a value WNL. In patients with low albumin levels, a corrected calcium value WNL is acceptable. In patients with abnormal TSH, if Free T4 is normal and patient is clinically euthyroid, patient is eligible.

Alliance A021602

Platelet Count $\geq 100,000/\text{mm}^3$

PT/INR, PTT < 1.3 x upper limit of normal (ULN)

AST/ALT $\leq 3 \text{ x ULN}$ Total Bilirubin $\leq 1.5 \text{ x ULN*}$

Creatinine $\leq 1.5 \text{ mg/dL } \mathbf{OR}$ Creatinine Clearance $\geq 45 \text{ mL/min}$

Albumin $\geq 2.8 \text{ g/dL}$

Potassium within normal limits (WNL)**

Phosphorus WNL**
Calcium WNL**
Magnesium WNL**

Urine Protein to Creatinine (UPC) Ratio ≤ 1

QTcF $\leq 500 \text{ msec}$ TSH WNL**

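### The hold-and-reduce order in 8.2.3.2 can fire at values that already meet its own release condition, and the 8.2.3.3 resume limit does not allow for the Gilbert exception at entry

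*Combined protocol and SAP*

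**What the plan says.** Section 8.2.3 of the protocol splits patients by their liver enzymes at registration.

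- **8.2.3.1** opens "8.2.3.1 For patients with ALT or AST" at or below ULN. At grade 1 it says "For grade 1 ALT or AST, continue cabozantinib/placebo and consider checking LFTs in two weeks". A hold followed by a one-level reduction starts only when the value keeps rising inside grade 2, or at grade 3.
- **8.2.3.2** opens "For patients with ALT or AST above the ULN but" no higher than "3.0 x ULN (i.e. grade 1) at the time of registration". After a 1.5-fold or greater increase with both enzymes at or below 5.0 x ULN, treatment continues at first. Then: "If LFTs continue to rise, delay cabozantinib/placebo (and consider checking LFTs weekly) until grade" is 1 or lower, and treatment resumes one level down.
- **8.2.3.3** covers all patients: "For ALT or AST increases accompanied by progressive elevations of total bilirubin and/or elevations of coagulation tests", treatment is held until total bilirubin and INR are each below 1.5 x ULN and ALT or AST is grade 1 or lower, then resumed one level down.

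Three other places bear on these rules. Section 8.2 states "Cabozantinib/placebo will not be re-escalated once reduced". It also tells sites to follow the stricter order when several apply, and to discontinue after a hold of more than 4 weeks. Section 8.2.1 gives two levels below the 60 mg start (40 and 20 mg). The footnote to the required laboratory values (3.2.9, repeated for re-registration in 3.3.3) relaxes the bilirubin limit: "Except in the case of Gilbert disease, in which case Total Bilirubin must be" no more than 3 x ULN.

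**The concern.** A hold needs a trigger and a release condition that cannot both be true of the same value. In 8.2.3.2 they can be. A site following the text then has a hold of no stated length, followed by a reduction that cannot be undone. In 8.2.3.3 the difficulty is reversed: for some Gilbert patients the release condition lies at or below the level at which they were admitted, so full recovery to entry values does not release the hold.

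At stake is dose received, and in the Gilbert case continued treatment, for reasons that come from the wording. Section 9.4 lists ALT and AST increases as possibly related to cabozantinib, so any effect plausibly falls more on the active arm. Sites may also differ in how they handle a hold whose end is undefined.

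**Working it through.** This is a check of rule logic; the plan gives no figure to reproduce.

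**Inputs, all from the protocol.** 8.2.3.2 labels values up to 3.0 x ULN as grade 1, and above 5.0 to 20.0 x ULN as grade 3; by implication, grade 2 is above 3.0 to 5.0. The fold trigger is 1.5. Release is at grade 1 or lower. *Assumption:* the increase is measured from the registration value, because the text names no reference.

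**Step 1: where trigger and release coincide.** Let b be the raised enzyme at registration in multiples of ULN, above 1.0 and up to 3.0. The trigger value is 1.5 x b. It lies within grade 1 when 1.5 x b ≤ 3.0, that is, b ≤ 3.0 / 1.5 = 2.0.

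| Baseline b | 1.5 x b | Still grade 1? |
|---|---|---|
| 1.2 | 1.80 | yes |
| 1.5 | 2.25 | yes |
| 1.9 | 2.85 | yes |
| 2.0 | 3.00 | yes, at the limit |
| 2.5 | 3.75 | no |
| 3.0 | 4.50 | no |

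The affected interval is (2.0 − 1.0) / (3.0 − 1.0) = half the width of the baseline range. This is a share of the range, not of patients. Inside it, a value that is still rising after the 1.5-fold point but has not passed 3.0 x ULN triggers the hold while the release condition is already true. Above b = 2.0 this does not occur.

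**Step 2: the parallel rule.** 8.2.3.1 ties its hold for a continuing rise to grade 2, so a value that triggers it cannot also meet release at grade 1 or lower. 8.2.3.2 has an upper bound (5.0 x ULN) but no matching lower one.

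**Step 3: overlap of the headings.** Each heading is met by one enzyme. ALT 0.8 and AST 1.2 x ULN satisfies both. The two orders for such a patient compare as follows:

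| On-treatment course | 8.2.3.1 | 8.2.3.2 |
|---|---|---|
| ≥ 1.5-fold, up to 5.0 x ULN, not rising further | continue | continue |
| ≥ 1.5-fold, up to 3.0 x ULN, still rising | continue | hold, then reduce |
| ≥ 1.5-fold, above 3.0 to 5.0 x ULN, still rising | hold, then reduce | hold, then reduce |
| ≥ 1.5-fold, above 5.0 to 20.0 x ULN | hold, then reduce | hold, then reduce |
| below 1.5-fold (e.g. 2.5 to 3.3, 1.32-fold), or above 20.0 x ULN | gives an order | silent |

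The orders conflict only in the second row. The stricter-order rule in 8.2 then selects 8.2.3.2, which is the circular case of Step 1.

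**Step 4: Gilbert patients.** Entry bilirubin may be up to 3 x ULN; resumption needs a value below 1.5 x ULN. For an entry value of 1.5 to 3 x ULN, returning to that value does not satisfy the release condition. The hold can be started by an ALT or AST increase with raised coagulation tests alone, so bilirubin need not have changed. If it stays at its entry level, the hold passes 4 weeks and 8.2 requires discontinuation.

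**The case against.** **Precedence.** A reader might infer from the overlapping headings that a patient with one normal and one raised enzyme receives opposite orders with nothing to choose between them. The documents do not support that. The stricter-order rule in 8.2 makes the choice, and the conflict is confined to one row of the table. What stands is that the rule sends the patient into the branch whose trigger and release coincide.

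**Grading.** Section 9.0 requires CTCAE v5.0, which is not reproduced, and the grade 1 label in the 8.2.3.2 heading describes registration values. This is a fair caution. The section's on-treatment grade 3 label is, however, also given in multiples of ULN, so reading its grades that way is the natural course. It can also be said that the order is workable as a short hold followed by a reduction, but the text does not say so.

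**Worst case.** A reader might infer that repeated triggers take a patient from 60 to 40 to 20 mg and then off treatment without exceeding 3 x ULN. That needs every increase to be measured from registration and a continuing rise each time. If each is instead measured from the preceding value and the rises compound without falling back, three of them give at least 1.5 x 1.5 x 1.5 = 3.375 times a baseline already above 1.0 x ULN.

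**Different rules by baseline.** A baseline-normal patient going from 0.9 to 2.9 x ULN (3.2-fold) continues under 8.2.3.1, with a recheck to be considered. Treating baselines differently is the purpose of two subsections and is not in itself a contradiction.

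**Impact.** Section 1.2.2 reports that 81% of phase II patients completing at least one cycle needed a reduction, with no relationship seen between dose modification and disease control or progression. Section 14.2.1 found no clear association between early versus late modification and reduced PFS in medullary thyroid cancer. Efficacy is analysed by intention to treat. No effect on the primary result can be claimed.

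**Gilbert.** The discontinuation rule in 8.2.3.3 excuses bilirubin elevations that have another explanation, which could cover Gilbert disease. The resume rule beside it has no such exception, so the point stands, though it is narrow.

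**Conclusion.** The concern holds as two defects of wording. First, in 8.2.3.2, for a baseline above 1.0 and up to 2.0 x ULN, a continuing rise still at or below 3.0 x ULN can order a hold whose release condition is already met, followed by a permanent one-level reduction. This rests on measuring the fold increase from registration and on the section's own ULN labels for grade. The heading overlap adds to it only by steering mixed-baseline patients into that branch. Second, a Gilbert patient enrolled at 1.5 to 3 x ULN and held under 8.2.3.3 can return to entry values, still not qualify to resume, and have to discontinue after 4 weeks.

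The documents give no frequency for mixed baselines, for rises of this kind or for Gilbert disease, so the number of patients affected is unknown. The passages should be corrected because, followed literally, they produce results that do not fit the protocol's other provisions; no bias in the efficacy comparison has been shown.

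**What to change.** Reconcile 8.2, 8.2.3 and the Gilbert footnote to the laboratory criteria:

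- State which of 8.2.3.1 and 8.2.3.2 applies when one enzyme is normal and the other raised, or that they apply enzyme by enzyme.
- State the reference value for the 1.5-fold increase.
- Word the 8.2.3.2 trigger and resume criterion so that both cannot be true of the same value.
- Reconcile the 8.2.3.3 bilirubin resume value with the Gilbert exception at entry and re-registration.

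The study team sets all values; none is proposed here. The cost is an amendment of a few sentences. No tests are added, because section 5.0 already schedules ALT, AST and bilirubin on Day 1 of each cycle and Day 15 of Cycles 1 and 2.

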8.2.4 Proteinuria

The UPC (urine protein to creatinine) Ratio directly correlates with the grams of protein found in a 24-hour urine. The UPC ratio based on a random urine sample can be used in place of a 24-hour urine. If the UPC Ratio is > 1, then a repeat UPC Ratio and a 24-hour urine protein and creatinine may need to be performed to confirm the result.

UPC Ratio = Urine Protein Concentration (mg/dL) Creatinine Concentration (mg/dL)

For UPC Ratio < 3.5 or urine protein < 3.5 g/24 hours, continue the same dose of cabozantinib/placebo.

For UPC Ratio \geq 3.5 or urine protein \geq 3.5 g/24 hours, delay cabozantinib/placebo and check UPC weekly until proteinuria resolves to UPC < 1.5 or urine protein < 1.5 g/24 hours, then resume cabozantinib/placebo with one dose level reduction. If treatment is delayed for more than one cycle (4 weeks) due to proteinuria, discontinue cabozantinib/placebo.

For Nephrotic Syndrome (proteinuria ≥ 3.5 g/24 hours in combination with hypoalbuminemia, edema, and hyperlipidemia) or other relevant renal disease, discontinue cabozantinib/placebo.

